# Secondary Objectives:

 To determine if the Activia™ reduces the incidence of diarrhea for mRCC patients treated with VEGF-TKIs.

We will compare the rate of all grade diarrhea in patients who receive the dietary supplement and those who do note. The rate of grade 3/4 diarrhea will also be compared between the two groups. A Fisher's exact test with a 0.050 one-sided significance level will have 80% power to detect the difference between the Activia™ group proportion with diarrhea, ②₁, of 0.200 and a non-Activia™ proportion, ②₂, of 0.800 when the sample size in each group is 10.

2) To compare pre-treatment levels of circulating Treg cells and levels of peripheral STAT3 in patients with and without diarrhea with sunitinib therapy, and correlate with Bifidobacterium, other bacteria, and Activia™:

Treg quantity is a secondary measurement and an analysis will be carried out to evaluate whether Tregs expression differs in patients who develop diarrhea with VEGF-TKI therapy as compared to patients who do not. The distribution of the Treg quantity will be examined and log transformation may be applied if the distribution is skewed. Parametric or nonparametric test will be used to compare Tregs between the the diarrhea and non-diarrhea groups, and between the Activia™ and non-Activia™ groups.

3) To determine if patients with the diarrhea in mRCC patients treated with VEGF-TKI therapy have a lower baseline level of *Bifidobacterium spp*.

IRB Protocol No. 16088 Version Date: 06/12/2020

Once diarrhea has occurred, the Bifidobacterium spp may be reduced. We will compare the abundance of Bifidobacterium spp. Between diarrhea and non-diarrhea patients and the change in Bifidobacteria in patients who subsequently get diarrhea.

4) To explore association between psychosocial symptoms (anxiety and depression) and bacteriomic profile and gastrointestinal toxicity in mRCC patients treated with VEGF-TKIs. We will dichotomize the population based on low or high depression (and subsequently low and high anxiety). Using descriptive statistics, we will then assess differences in response rates, gastrointesntinal toxicity, microbial diversity and immune biomarkers.

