oncologist may consider toxicity. Diarrhea appears to be particularly problematic with VEGF-TKI therapy, for example sunitinib nearly 50% of patients reporting some degree of diarrhea, usually first occurring within the first two cycles of therapy, and 10% of patients developing grade 3/4 toxicity (i.e., toxicities warranting dose modification or treatment discontinuation). In contrast, few patients experience severe diarrhea in association with bevacizumab therapy. The phenomenon of diarrhea appears to be quite consistent across VEGF-TKIs, as seen in Table 1. Notably, even VEGF-TKIs used in the second line setting, such as axitinib, yield similar rates of diarrhea. The frequency of diarrhea encountered with these agents is quite startling.

Table 1. Frequency of diarrhea reported in pivotal phase III trials assessing VEGF-TKIs for mRCC.1,2,3

Agent	N	Grade 1 or 2	Grade 3 or 4	Overall
Sorafenib	451	41%	2%	43%
Sunitinib	375	52%	9%	61%
Pazopanib	290	48%	4%	52%
Cumulative	1116	47%	5%	51%

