# 2.2 Overview and rationale of study design

Diarrhea is a significant toxicity experienced by roughly 50% of patients treated with VEGF-TKIs. Identifying a pre-treatment biomarker associated with treatment-related diarrhea may lead to the development of a pre-treatment conditioning regimen. Data from our pilot study in metastatic renal cell carcinoma (mRCC) patients undergoing VEGF-TKI therapy demonstrated a notably low abundance of Bifidobacterium spp. The primary objective of this study will be to ascertain whether or not the simple addition of Activia™ yogurt (containing Bifidobacterium lactis DN-173 010) will reduce this dysbiosis. Changing the abundance of this species, and indirectly other species in the complex microbiota population prior to initiating therapy may decrease in VEGF-TKI related diarrhea.

Twenty patients with mRCC will be recruited prior to initiating standard of care therapy with VEGF-TKIs, and will be followed for three months of therapy for specimen and data collection. Patients will be treated according to NCCN guideline recommendations for each VEGF-TKI agent. An intervention will be performed. Specifically, patients will be randomized to either a probiotic-supplemented group (Activia™) or a probiotic-restricted group using a permuted block design to ensure the 20 patients were assigned to the two groups with 1:1 ratio. Patients in the probiotic-supplemented group will be asked to consume one 4 oz serving of Activia vanilla yogurt in the evening daily for the 3 month study period and patients in the probiotic-restricted group will be asked to avoid any intake of yogurt or yogurt-containing foods for the evaluation period of the study.

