Several stool collections will be performed. Stool samples will be collected prior to initiating VEGF-TKI treatment, one week after initiating therapy, two weeks after initiating therapy, three weeks after initiating therapy (i.e. after the first week off of therapy), three months (13 weeks) into VEGF-TKI therapy, and at the onset of diarrhea. A stool specimen at the onset of diarrhea would reflect changes in the bacteriome that could potentially drive onset of this symptom. Compliance with stool submission has not been an issue in our pilot study (IRB 12096). All stool samples will be collected by the participant at home and sent via overnight shipping to the laboratory at City of Hope. Participants will receive training on the sample collection process. Participants will also be asked to complete a diet log and stool frequency log that uses the CTCAE v4.0 definitions of diarrhea:

IRB Protocol No. 16088 Version Date: 06/12/2020

- Grade 1: Increase of <4 stools per day over baseline; mild increase in ostomy output compared to baseline
- Grade 2: Increase of 4 6 stools per day over baseline; moderate increase in ostomy output compared to baseline
- Grade 3: Increase of >=7 stools per day over baseline; incontinence; hospitalization indicated; severe increase in ostomy output compared to baseline; limiting self care ADL
- Grade 4: Life-threatening consequences; urgent intervention indicated
- Grade 5: Death

For purposes of the current study, we are interested in characterizing the incurrence of all grade diarrhea (e.g., grade 1-5 toxicity); however, the grade of diarrhea incurred will be specified.

From the serial stool samples, *Bifidobacterium spp*. levels and stool bacteriomic profile over time will be assessed and associations will be examined between patients who experience diarrhea and those who do not.

To explore potential confounding factors or associations of interest between the bacteriomic profile and the presence of diarrhea, data collection will include: intake of yogurt, general description of daily diet, prior anti-cancer therapies, concomitant medications during the study period, and response to VEGF-TKIs. These data will be collected from the participant's medical record or from the participant's daily log.

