#### 5.0 CLINICAL DATA COLLECTION

#### 5.1 Participant Daily Diary

Participants will be oriented to complete the daily study log, found in Appendix B. The log will be collected and reviewed during visits to the clinic at the end of each 3-week treatment regimen (weeks 3, 6, 9 and 13 of treatment). The following information from the diary will be entered into the study specific database for analysis:

- Diarrhea, categorized per CTCAE 4.0 diarrhea grading. Please note that the patient will be instructed to consider diarrhea to be an increase in stool frequency of < 4 over baseline. This definition is consistent with the CTCAE 4.0 terminology for grade 1 diarrhea.
- Stool specimen collection dates
- Yogurt intake, or intake of yogurt-containing foods

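### The 80% power for the diarrhea comparison assumes an unsourced 80% diarrhea rate without Activia; at the protocol's cited rates of 43% to 61%, power to detect a fall to 20% is 16% to 44%

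*Combined protocol and SAP*

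**What the plan says.** Section 8.1, under the first secondary objective, compares all-grade diarrhea between the arms. It states that Fisher's "exact test with a 0.050 one-sided significance level will have 80% power to detect the difference between the" Activia proportion of 0.200 and a non-Activia proportion "of 0.800 when the sample size in each group is 10". No source is given for either proportion.

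The background sections give these all-grade rates:

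- Section 2.2: "Diarrhea is a significant toxicity experienced by roughly 50% of patients treated with VEGF-TKIs".
- Section 2.1, text, on sunitinib: "nearly 50% of patients reporting some degree of diarrhea, usually first occurring within the first two cycles of therapy".
- Section 2.1, Table 1 ("Frequency of diarrhea reported in pivotal phase III trials assessing VEGF-TKIs for mRCC"): sorafenib 43% (N = 451), sunitinib 61% (N = 375), pazopanib 52% (N = 290), cumulative 51% (N = 1116).

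The pilot study description in Section 2.1 gives no diarrhea rate. The trial's endpoint is on the same all-grade basis: Section 2.2 says "we are interested in characterizing the incurrence of all grade diarrhea".

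**The concern.** A power statement tells the reader what a trial can detect. This one rests on a control rate 19 points above the highest rate in the protocol (80% against 61%) and 29 points above the cumulative rate (80% against 51%). If about half of control patients have diarrhea, the assumed 60-point fall cannot occur, because the largest possible fall is about 50 points.

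Reducing diarrhea is the first secondary objective listed in Section 1.0 and the clinical reason for the intervention. It is also the only secondary objective with a power figure. A non-significant result read against 80% power could be taken as evidence that Activia does not reduce diarrhea, when the trial would probably have missed even a large reduction.

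**Working it through.** **Inputs.** From Section 8.1: one-sided Fisher's exact test, alpha 0.05, 10 per arm, Activia rate 0.20, control rate 0.80. From Table 1: control rates 0.43 (lowest), 0.51 (cumulative) and 0.61 (highest). The cumulative figure checks: (451 × 0.43 + 375 × 0.61 + 290 × 0.52) / 1116 = 51.4%.

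**Formula.** Let a and c be the numbers with diarrhea among 10 Activia and 10 control patients. The one-sided p-value is the hypergeometric probability of a or fewer Activia events given a + c events in 20 patients. Power is the sum of Bin(a; 10, pA) × Bin(c; 10, pC) over all pairs (a, c) in the 11 × 11 table with p ≤ 0.05.

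**Step 1: the plan's own figure.** With pA = 0.20 and pC = 0.80, power = 0.805. The stated 80% is reproduced.

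**Step 2: what the test requires.**

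| Controls with diarrhea (of 10) | Most Activia cases allowed for p ≤ 0.05 |
|---|---|
| 3 or fewer | never significant |
| 4 or 5 | 0 |
| 6 | 1 |
| 7 | 2 |
| 8 | 3 |

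For example, 0 against 5 gives p = 0.016, but 1 against 5 gives p = 0.070. At the planned 8 of 10 controls there is room for 3 Activia cases (p = 0.035). At 5 of 10, about the rate the protocol cites, there is room for none.

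**Step 3: power at the protocol's control rates.** The documents do not say how the effect should carry over to a lower control rate, so four versions are shown.

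| Effect carried over as | Control 43% | Control 51% | Control 61% |
|---|---|---|---|
| Activia fixed at 20% | 16.2% | 26.9% | 44.4% |
| Same relative risk, 0.20/0.80 = 0.25 | 32.5% | 41.9% | 54.9% |
| Same odds ratio, (0.20/0.80)/(0.80/0.20) = 1/16 | 50.6% | 60.9% | 70.5% |
| Diarrhea halved | 14.4% | 18.7% | 25.5% |

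None reaches 80%. In the first row the chance of a non-significant result is 1 − 0.162 = 84%, 1 − 0.269 = 73% and 1 − 0.444 = 56%.

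**Step 4: what 80% power would take.**

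- With Activia at 20%, the control rate must be at least 79.7%.
- With 10 per arm, the Activia rate must be about 1.0% at a 51% control rate, or about 5.4% at 61%. At 43% it cannot be reached: zero risk on Activia gives 69%.
- For a fall to 20%, the size per arm would be 58, 35 or 22 at control rates of 43%, 51% or 61%.

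**Step 5: if the daily log raises the control rate.** These higher rates are assumptions, with Activia at 20%: 65% gives 52.2%, 70% gives 62.2% and 75% gives 71.8%.

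**The case against.** There are four fair counter-arguments.

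- **The sentence is conditional and true.** With the sample size fixed at 20, it can be read as naming the difference that 10 per arm can detect, and a 60-point difference already signals a weak comparison. The arithmetic does stand. But the text never sets that difference against the background rates, so the reader is not told that it cannot arise at a control rate near 50%.
- **Table 1 is not this trial's endpoint.** Its rates come from phase III reporting. Here patients keep a daily log, and Section 5.1 says "the patient will be instructed to consider diarrhea to be an increase in stool frequency of < 4 over baseline", with no minimum duration. One day with one to three extra stools could count, so the control rate may run higher. This stands as a limit on certainty. It does not support 0.80, because the protocol neither makes the argument nor gives a log-based rate, and the rate would have to reach about 80% for the claim to hold.
- **The 16% to 44% range is one of several.** It keeps Activia at 20% and lowers only the control rate. Keeping the relative risk or the odds ratio gives higher figures. This is correct, but the conclusion is the same in each version.
- **It is a secondary objective.** Neither the sample size in Section 8.2 nor the primary power statement depends on it. This stands and limits the weight of the point.

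**Conclusion.** The concern holds. The 80% is computed correctly from an input that the protocol does not source and that its own figures contradict. On those figures, power to detect a fall to 20% is about 27% at a 51% control rate, and 16% to 44% over 43% to 61%. Even the most favorable way of carrying the planned effect over reaches only 51% to 71%.

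These results assume that all 10 patients per arm are evaluable, since no dropout allowance is stated. They also assume that the Table 1 rates are a fair guide. The table covers sorafenib, sunitinib and pazopanib; Section 2.1 calls axitinib similar and gives no rate for cabozantinib.

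This should be fixed because a stated power figure misleads as it stands. The primary analysis is not affected.

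**What to change.** Either cite the source of the 0.80 control rate, such as a log-based rate under the Section 5.1 definition, or replace the power sentence with wording along these lines:

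> *With 10 per arm and a control rate of about 51% (range 43% to 61%), the one-sided Fisher's exact test has about 27% (16% to 44%) power to detect a reduction to 20%. It reaches 80% only if the Activia rate is about 1% at a 51% control rate, or about 5% at 61%. If daily logging raises the control rate to between 65% and 75%, power to detect a reduction to 20% is 52% to 72%.*

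Two optional additions would help the reader of a null result: label the comparison exploratory, and report the risk difference with an exact confidence interval.

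The cost is protocol wording and a less favorable stated power. No patients, data collection or primary analysis change.

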#### 4.0 STUDY ACTIVITY TABLE

# 4.1 Study Activity Table

	Screeninga Pre-tx		VEGF-TKI treatment b				
	Screening a	FIE-LX	Wk 1	Wk 2	Wk3	Wk 4	Wk 13
Informed consent C	Х						
Eligibility review d	Х						
Registration e	Х						
Participant orientation f		xf					
Research blood collection g		χg			χg		χg
Planned stool specimensh		χi		χj	χj	χj	χj
Stool specimen at onset of diarrheah			Xk				
Study log review/collection					χl		χl
Data collection m			Х		Х		Х
Dietary intervention n		χn		χn	χn	χn	χn
PHQ-9 and GAD-7 °		X					X

- a. Screening procedures are to occur prior to research sample collection with the following caveat: If the sample is collected on the same day as completion of eligibility review, the informed consent and eligibility review must precede sample collection; registration must occur that very day but may be before or after sample collection.
- b. Participants who end vascular endothelial growth factor tyrosine kinase inhibitor (VEGF-TKI) treatment prior to Week 13 will jump to the 'Week 13' assessments which will be performed within 1 week of the decision to end VEGF-TKI treatment.
- c. Informed consent to occur before any study specific screening procedures.
- d. Inclusion/exclusion criteria are found in Section 3.2. Source documentation providing investigator's confirmation that patient has met all eligibility criteria must be available prior to registration.
- e. Registration into MIDAS.
- f. Participants will receive training on completion of the diet log, stool frequency log, and stool specimen collection SOP by the clinician investigator. This education will be noted in the medical record.

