- g. One sample of blood for research will be collected within 7 days before start of VEGF-TKI, at Week 3 (+/- 1 week), and at Week 13. Efforts will be made to collect the sample at the time of routine blood sample collection. Blood will be collected into 10 mL CPT vacutainer tube, inverted slowly about 8-10 times, maintained at RT and transported to pathology laboratory, who will ensure the sample is labeled with the "COH IRB #16088", the participants RPN, and time and date of collection, prior to transport to the [name] laboratory. The [name] laboratory should be notified of planned samples via email ([contact] or other designee) preferably at least a day in advance of sample collection. The sample should be brought to the [name] as soon as possible for processing to begin within 4 hours of the time of collection.
- h. All stools samples to be collected at home and dropped off the same day to a FedEx location prior to that day's FedEx pick-up, per Stool Collection SOP (Appendix A).
- i. Pre-treatment stool samples to be collected within 7 days of start of VEGF-TKI.
- j. Week 2, Week 3, Week 4, and Week 13 stool samples to be provided any day Monday to Thursday on the designated week.

IRB Protocol No. 16088 Version Date: 06/12/2020

- k. If diarrhea is not incurred, submission of stool is not required. Sample to be collected as early as possible after the onset of diarrhea such that the sample can be collected and delivered to FedEx drop off (Monday-Thursday only).
- I. Efforts will be made to review and/or collect the study log with participants on weeks 3, 6, 9, and 13 which correspond to the times when patients taking VEGF-TKI are usually seen (and assessed with CBC w/ dif and serum chemistry) after three weeks of treatment. It will not be a deviation if the visits to review/collect study logs are delayed or combined.
- m. Data will be collected and entered into eCRFs from the participant provided logs and the medical record. Data to be collected within two weeks of the end of the defined study point.
- n. If patients are randomized to the probiotic-supplemented group, they will be asked to purchase Activia vanilla yogurt. Patients will be asked to consume one 4 oz serving of Activia vanilla yogurt in the morning and one 4 oz serving of Activia vanilla yogurt in the evening beginning Week 2 and through Week 13.

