#### 6.3 Sample Analysis

Analysis of samples for Treg, STAT3 and MDSC will occur in the laboratory of [name]. Relevant WBC subsets will be conducted through previously reported techniques. PBMCs will be immersed in a mixture of PBS, 2% FCS and 0.1% (wt/vol) sodium azide with Fc III/IIR-specific antibody to block nonspecific binding and stained the cells with different combinations of fluorochrome-coupled antibodies to CD11c, I-Ab (MHC class II), CD86, CD11b, Gr1, CD49b, CD3, CD25 or Lag-3, or with annexin V (BD Biosciences). We collected fluorescence data on FACSCalibur (Beckton Dickinson) and analyzed them using FlowJo software (Tree Star). This method has been previously published by Chalmin *et al.*

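### The only time point given for the between-arm Treg test is pre-treatment, where it may say nothing about Activia, and no analysis is specified for the on-treatment immune samples.

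*Combined protocol and SAP*

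**What the plan says.** Section 8.1, secondary objective 2, is headed "To compare pre-treatment levels of circulating Treg cells and levels of peripheral STAT3 in patients with and without diarrhea with sunitinib therapy", with a further clause about correlating these with bacteria and Activia. Section 1.0 has the same objective, worded for VEGF-TKI therapy in general.

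The paragraph under the heading names one marker: "Treg quantity is a secondary measurement and an analysis will be carried out to evaluate whether Tregs expression differs" by diarrhea status. It allows a log transformation if the data are skewed and ends: "Parametric or nonparametric test will be used to compare Tregs between the the diarrhea and non-diarrhea groups, and between the Activia™ and non-Activia™ groups". It gives no visit, significance level or sidedness, and does not mention STAT3 or MDSC.

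Section 4.1 footnote g has research blood "collected within 7 days before start of VEGF-TKI, at Week 3 (+/- 1 week), and at Week 13". Section 2.2 describes comparing pre-treatment Treg, MDSC and STAT3 by diarrhea status and then says that three blood samples are provided for these analyses.

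On the intervention, Section 4.1 footnote n has patients take "Activia vanilla yogurt in the evening beginning Week 2 and through Week 13". The dietary intervention row of the activity table is also marked in the pre-treatment column.

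**The concern.** The item combines two different questions. Whether pre-treatment Treg differs between patients who do and do not go on to have diarrhea is a predictive-biomarker question, and the pre-treatment sample is the right one for it. Whether Activia changes Treg is an intervention question, and it needs a sample taken after the yogurt has started.

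The plan puts the between-arm test under the first question's heading and gives it no visit of its own. An analyst who follows the heading would compare the arms on blood that, under footnote n, predates the yogurt. A small p-value would be a chance imbalance and could be reported as an effect of Activia. A large one would say nothing about Activia. The samples that could address the question are scheduled, but no analysis is set out for them.

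**Working it through.** **1. Which visit applies?** The documents give no power or level for the Treg analysis, so there is no stated figure to reproduce. The question is one of text first:

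| Place | Content | Visit |
|---|---|---|
| Section 1.0 and the item 2 heading in 8.1 | Treg and STAT3 by diarrhea status | Pre-treatment |
| Section 2.2 | Treg, MDSC and STAT3 by diarrhea status | Pre-treatment |
| Item 2 analysis paragraph in 8.1 | Treg by diarrhea status and by arm | None given |
| Item 4 in 8.1 | Unnamed immune biomarkers by depression and anxiety group, descriptive | None given |
| Section 4.1 footnote g; Section 6.1 | Blood draws | Pre-treatment, Week 3, Week 13 |

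Pre-treatment is the only visit tied to a Treg analysis. Week 3, Week 13 and change from pre-treatment appear in no immune-marker analysis.

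**2. What a pre-treatment test by arm can show.** If yogurt starts at Week 2, arm is assigned at random and cannot have affected the earlier sample. The null hypothesis is then true by design, and P(reject) equals the level of the test. Simulated check with 20,000 runs, 10 per arm, log-normal values (an assumption) and no arm effect, at 0.05:

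- t-test on logs: 4.9% one-sided, 5.2% two-sided.
- Exact Mann-Whitney: 4.3% one-sided, 4.6% two-sided.

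No effect of Activia, however large, would move these figures.

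**3. If the visit is instead taken as open.** The analyst then chooses after seeing the data. Simulation with no arm effect, 10 per arm, normal values on the log scale, two-sided t-tests at 0.05, and assumed between-visit correlations of 0.3, 0.5 and 0.7:

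- At least one significant result among three visits: 13.7%, 12.5% and 11.3%.
- Adding the two changes from pre-treatment: about 18% at each correlation.

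**4. What an on-treatment comparison could detect.** Two-sample t-test with n per arm: df = 2n − 2 and noncentrality = d/√(2/n). With n = 10 and one-sided 0.05, the critical value is t(0.95, 18) = 1.734. At d = 1.156 the noncentrality is 1.156/√0.2 = 2.585, and power is 0.80. Detectable d for 80% power:

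| Evaluable per arm | One-sided 0.05 | Two-sided 0.05 |
|---|---|---|
| 10 | 1.16 SD | 1.32 SD |
| 9 | 1.22 SD | 1.41 SD |
| 8 | 1.31 SD | 1.51 SD |

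The one-sided 0.05 is the primary analysis's level; none is stated for Treg. Adjusting for the pre-treatment value multiplies the detectable difference by about √(1 − r²), where r is the correlation between the two visits. The documents do not give r. For r = 0.3, 0.5 and 0.7, 1.16 becomes 1.16 × 0.954 = 1.11, 1.16 × 0.866 = 1.00 and 1.16 × 0.714 = 0.83 SD of the on-treatment value, ignoring the one degree of freedom spent. No assay SD is given, so these cannot be put in assay units.

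**The case against.** The strongest objection is that the plan never says the between-arm test uses the pre-treatment blood. The sentence has no visit, and the heading's closing clause about Activia could be read as reaching beyond pre-treatment levels. This stands to the extent that the reading is the natural one, not the only one. A reader might infer that the plan commits itself to a test of randomisation alone; the text does not go that far. But the other reading, an open visit, leaves the choice to be made after the data are seen.

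Second, pre-treatment means before VEGF-TKI, not necessarily before yogurt. The pre-treatment mark in the activity table conflicts with footnote n, and Section 2.2 speaks of changing the flora before therapy begins. This also stands: the uninformative-test conclusion depends on footnote n. Even with an earlier start, though, a pre-treatment sample would reflect at most the first days of exposure.

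Third, a reader might infer that the Week 3 and Week 13 bloods have no stated use. Section 2.2 contradicts that by tying all three draws to these analyses. What is missing is a specified analysis.

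Fourth, a reader might infer from the antibody list in Section 6.3 that STAT3 is not assayed. The documents do not support this. Section 6.2 names pSTAT3 as assessed in the protocol, and Section 6.3 names STAT3 and relies on previously reported techniques. STAT3 also has a stated comparison by diarrhea status in Section 2.2 and in the item heading; only its method is absent.

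**Conclusion.** The concern holds in a limited form. The between-arm Treg comparison has no visit except the pre-treatment one in its heading. If that blood is used and yogurt starts at Week 2, the test rejects at its nominal level whatever Activia does. If the visit is left open, the chance of at least one false positive over three visits is about 11% to 14%, under the assumed correlations. No on-treatment or change analysis of Treg, STAT3 or MDSC is specified, although the blood is scheduled.

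The conclusion about the pre-treatment test rests on footnote n, which the activity table contradicts. The primary endpoint, the diarrhea comparison by arm and the pre-treatment comparison by diarrhea status are not affected. This is a secondary, correlative analysis in 20 patients, so the change is worth making but is not critical to the trial.

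**What to change.** Split item 2 of Section 8.1.

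- (a) Compare pre-treatment Treg, STAT3 and MDSC by diarrhea status, as planned.
- (b) Compare Activia with non-Activia on log-Treg at Week 13 as the one main time point, by a linear model adjusted for pre-treatment log-Treg, with level and sidedness stated. Make Week 3 supportive: under footnote g its window of plus or minus one week can fall in Week 2, when footnote n starts the yogurt. Section 6.1 sets the window after Week 13 instead, so align the two. Label STAT3 and MDSC by arm as exploratory, so that three markers at two visits do not become six tests of equal standing.

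State how early stoppers are handled, because Section 4.1 footnote b moves their Week 13 assessments to the time VEGF-TKI ends. The sponsor must also reconcile the pre-treatment mark on the dietary row with footnote n; which is intended is not for this review to say.

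The cost is SAP wording and a little more analysis on blood already in the schedule, with no added draw. The comparison will still be imprecise: about 1.16 SD detectable unadjusted with 10 evaluable per arm, and about 1.31 SD with 8. Report it as an estimate with a confidence interval, and do not read a non-significant result as no effect.
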